6.4.3. Medical History

Medical history is defined as any condition, with the exception of the study indication, that the subject may have prior to enrollment in the study, including any chronic conditions diagnosed prior to entry into the study. Non-serious AEs with onset after signing ICF but before the first dose (Part A) or randomization (Part B) will be included as medical history.

Medical history will be coded using the Medical Dictionary for Regulatory Activities (MedDRA) using the latest MedDRA dictionary around the time of Database Lock and will be presented by System Organ Class (SOC) and Preferred Term (PT) and total. The SOCs and PTs are to be sorted by Internationally Agreed order SOCs and descending PTs in the total column.

Medical history records will be summarized for the FAS for Part A (overall) and for Part B by treatment group and overall as follows:

- The number and percentage of subjects with at least one medical history record will be presented.
- The number and percentage of subjects with at least one medical history record within each primary SOC and PT will be presented. The summary will be sorted using the internationally agreed order for SOC and using descending order of overall numerical counts for PT. Where terms tie, these will be sorted alphabetically.

Medical history records will be listed by-subject and within-subject by medical history start date for the FAS.

6.4.4. Prior and Concomitant Medications

All medications will be coded using the WHO Drug Global Dictionary, Format B3 using the latest version around time of database lock, Anatomical Therapeutic Chemical (ATC) Classification codes.

Prior medications and concomitant medications are defined as follows:

- Prior medications are those taken with a stop date prior to the start of the Treatment Period.
- Concomitant medications are those with a start date and time on or before the end of the Treatment Period and a stop date on or after the start of the treatment period, including prior medications that are ongoing at the start of the treatment period.

See Section 5.2.3 for imputation of missing or partial dates for medication.

Prior and concomitant medications will be summarized separately for the FAS for Part A (overall) and Part B by treatment group and overall as follows:

- The number and percentage of subjects with at least one prior/concomitant medication will be presented.
- The number and percentage of subjects with at least one prior/concomitant medication within each Anatomical Group (ATC Level 1), Therapeutic Subgroup (ATC Level 2), and preferred term will be presented. The summary will be sorted using numerical counts by descending order of Anatomical Group, then descending order of Therapeutic Subgroup, then descending order of preferred term in the total column. Where groups or terms tie these will be sorted alphabetically.

Prior medications and concomitant medications will be listed separately for the FAS. In the listings the relative start and stop day of prior/concomitant medication use will be calculated relative to the first dose date and time of study drug and will be presented for those subjects who received at least one dose of study drug. If the concomitant medication is "Ongoing" it will be indicated as such in the listing and the relative stop day will not be calculated. Only original dates will be presented in the listing even though the relative day may be based on an imputed date.

6.5. Measurements of Study Drug Compliance

Study Drug compliance is defined as the number of doses that were actually taken relative to the number of doses that should have been taken as per the protocol for the planned duration of treatment exposure. A partial dose in CRF will be treated as a half dose. Study drug compliance in Part B will be summarized for period 1 and period 2 separately.

In general, the percentage of overall compliance, assessed by dose count, will be calculated as follows:

For Part A

For Part B Period 1

For Part B Period 2

For Part A, the total number of doses expected to be administered from Week 0 to Week 31 is 32 for all subjects. For Part B, the total doses expected to be administered differs by treatment assignment: for QW dosing, the total doses expected to be administered is 16 for Period 1 and 16 for Part 2; for Q2W dosing, the total doses expected to be administered is 8 for Period 1 and 8 for Part 2.

The calculated percentage compliance will be categorized as:

- < 80% compliance
- $\geq 80\%$ compliance

Compliance will be summarized for the Safety Analysis Set for Part A (overall) and for Part B by treatment group and Period as follows:

- Number of doses will be presented by default summary statistics.
- Percent compliance will be presented by default summary statistics.
- Number and percentage of subjects within each of the compliance categories will be presented. Treatment compliance will be listed for the Safety Analysis Set. Missing data will not be imputed and only original data for those fields (for example, date fields) will be presented in the listing together with derived variables such as the calculated compliance (%) and exposure duration.

6.6. Efficacy

Primary, secondary and exploratory endpoints will be presented by study part, timepoint and, for Part B, randomized treatment group. Observed data for binary endpoints, with NRI, will be presented with 2-sided 95% confidence intervals calculated using asymptotic Wald method. Observed data for continuous endpoints, with no imputation for missing values, will be presented with 2-sided confidence intervals calculated using normal approximations.

No statistical hypotheses will be tested in Part A of this study.

Hypotheses tested using data from Part B will be adjusted to control the family-wise error rate in the strong sense at $\alpha = 0.050$, two-sided. An adjustment of 0.0001 will be made to account for the unblinded data summaries reviewed by the DMC. The hypotheses will therefore be tested at $\alpha = 0.0499$.

The statistical comparisons in Part B for the primary efficacy endpoint and the secondary endpoints, all at Week 16, will be carried out in sequential order. The primary endpoint, comparing izokibep dosed QW to placebo dosed QW or Q2W, will be tested first, with significance concluded if p < 0.0499. If significant, the primary endpoint, comparing izokibep dosed QW or Q2W will be tested next, with significance concluded if p < 0.0499. If significant, the primary endpoint, comparing izokibep dosed Q2W to placebo dosed QW or Q2W will be tested next, with significance concluded if p < 0.0499. Testing of secondary endpoints will only be carried out if all prior tests, including both tests of the primary endpoint, first show significance with p < 0.0499. As long as all prior tests are significant, testing will proceed in the following order:

- The first secondary endpoint, proportion of subjects who experience ≥ 1 disease flare through 16 weeks of treatment, comparing izokibep dosed QW to placebo dosed QW or Q2W.
- The first secondary endpoint, proportion of subjects who experience ≥ 1 disease flare through 16 weeks of treatment, comparing izokibep dosed Q2W to placebo dosed QW or Q2W.
- The second secondary endpoint, achieving AN count of 0, 1, or 2 at Week 16 among subjects with baseline Hurley Stage II, comparing izokibep dosed QW to placebo dosed QW or Q2W.
- The second secondary endpoint, achieving AN count of 0, 1 or 2 at Week 16 among subjects with baseline Hurley Stage II, comparing izokibep dosed Q2W to placebo dosed QW or Q2W.
- The third secondary endpoint, proportion of subjects who achieve at least 3 points reduction from baseline in NRS at Week 16 among participants with baseline NRS ≥4, comparing izokibep dosed QW to placebo dosed QW or Q2W.
- The third secondary endpoint, proportion of subjects who achieve at least 3 points reduction from baseline in NRS at Week 16 among participants with baseline NRS ≥4, comparing izokibep dosed Q2W to placebo dosed QW or Q2W.

If a null hypothesis is not rejected, p-values for subsequent hypotheses in the sequence will be reported as nominal, and will not be used to assess objectives or make determinations of efficacy.

For Part B, efficacy endpoints will be summarized by Period 1 and Period 2 separately. For Period 2, in general, no hypothesis test will be performed and p-value will not be reported. For binary endpoints, stratified tests will use the four strata from the randomization process. If a subject was incorrectly classified during the randomization process, the analysis will use the correct classification as recorded in EDC, not the classification used during randomization as recorded in IRT.

For each primary and secondary efficacy endpoint, the number and proportion of subjects achieving the endpoint in each treatment group will be reported by stratum and overall. Confidence intervals will be present with stratification (CMH weighting) and without stratification (Wald method). P-values will be reported for the stratified analysis. A bar graph showing the proportion of subjects achieving the endpoint for each treatment group along with the associated p-value will be produced. Results will also be listed.

6.6.1. Primary Efficacy Analysis

The primary efficacy variable is defined as HiSCR75, the proportion of subjects who achieve at least a 75% reduction from baseline in the total AN count, with no increase from baseline in abscess or draining fistula count at Week 16 (comparing to baseline).

For Part B, the statistical null and alternative hypotheses to be used to assess the primary objective are:

> H₀: $\pi_{ABY} - \pi_{PBO} = 0$ H_A: $\pi_{ABY} - \pi_{PBO} \neq 0$

where π_{ABY} and π_{PBO} are the proportion of subjects achieving HiSCR75 at Week 16 among subjects randomly assigned to receive izokibep and placebo, respectively. One set of hypotheses will be tested for each dosing frequency of izokibep.

The treatment policy strategy approach for the estimand will be used in general, so subjects will be included using observed data at Week 16 regardless of treatment compliance, use of rescue medications or procedures except as noted below, or any other protocol deviations. Subjects with missing HiSCR75 assessments at Week 16 will be imputed as non-responders (non-response imputation or NRI). A composite strategy will be used for intercurrent events of receiving oral antibiotic therapy that could affect HS. A list of all oral antibiotic therapy that results in such imputation will be finalized after review of all oral antibiotic therapy received by any subject and before unblinding of the study and will include tetracycline, clindamycin, and possibly other products. Such subjects will be imputed using NRI. The Page 37 of 75 Final, Version 3.0, 03APR2024

ST-AD-008 version 06

number of subjects imputed with NRI will be tabulated with reasons for imputation at Week 16. Additionally, any lesions that received lesional incision and drainage or intralesional steroid injection will be counted as continuing to exist in the AN count, even if fully healed, at all later timepoints.

The null hypothesis of equal response rates will compare each dosing regimen of izokibep to the combined placebo group.

A stratified test of response rates will be used for the primary analysis. Within each of the four strata used for randomization, the response rate for each treatment group and corresponding standard error will be calculated. The difference in response rates (risk difference) will be calculated for each stratum. The common risk difference among the four strata and associated standard error will be estimated by combining the observed risk differences using Cochran-Mantel-Haenszel weighting. The estimated risk difference divided by the standard error will be used as the test statistic and a p-value calculated assuming that the test statistic follows a standard normal distribution under the null hypothesis. Analyses at earlier timepoints when data to calculate the HiSCR75 are collected will also be presented using the same methodology. P-values from earlier timepoints will be presented for descriptive purposes, not part of the alpha-preserving multiple testing strategy. No P-values after Week 16 will be presented.

Sample SAS code with stratification factors of comparing each dosing regimen of izokibep to the combined placebo group is given as following:

```
ods output commonpdiff = ;
proc freq data= ;
tables stratum * treatment * response / cmh commonriskdiff (test=mh cl=mh);
weight count / zeros;
run;
```

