9.1.1. Multiplicity Adjustment and Type I Error Rate

No alpha-controlled testing will be reported using any data from Part A of the study. Hypotheses tested using data from Part B will be adjusted to control the familywise error rate in the strong sense at $\alpha = 0.050$, two-sided.

As described in Section 9.4, an adjustment of 0.0001 will be made to account for the unblinded data summaries reviewed by the DMC. The hypotheses will therefore be tested at $\alpha = 0.0499$.

The statistical comparisons in Part B for the primary efficacy endpoint and the secondary endpoints, all at Week 16, will be carried out in sequential order. The primary endpoint, comparing izokibep dosed QW to placebo dosed QW or Q2W, will be tested first, with significance concluded if p < 0.0499. If significant, the primary endpoint, comparing izokibep dosed Q2W to placebo dosed QW or Q2W will be tested next, with significance concluded if p < 0.0499.

Testing of secondary endpoints will only be carried out if all prior tests, including both tests of the primary endpoint, first show significance with p < 0.0499. As long as all prior tests are significant, testing will proceed in the following order:

- The first secondary endpoint, HiSCR90 at Week 16, comparing izokibep dosed QW to placebo dosed QW or Q2W.
- The first secondary endpoint, HiSCR90 at Week 16, comparing izokibep dosed Q2W to placebo dosed QW or Q2W.
- The second secondary endpoint, HiSCR100 at Week 16, comparing izokibep dosed QW to placebo dosed QW or Q2W.
- The second secondary endpoint, HiSCR100 at Week 16, comparing izokibep dosed Q2W to placebo dosed QW or Q2W.
- The third secondary endpoint, HiSCR50 at Week 16, comparing izokibep dosed QW to placebo dosed QW or Q2W.
- The third secondary endpoint, HiSCR50 at Week 16, comparing izokibep dosed Q2W to placebo dosed QW or Q2W.
- The fourth secondary endpoint, proportion of subjects who experience flare, comparing izokibep dosed QW to placebo dosed QW or Q2W.
- The fourth secondary endpoint, proportion of subjects who experience flare, comparing izokibep dosed Q2W to placebo dosed QW or Q2W.
- The fifth secondary endpoint, achieving AN count of 0, 1 or 2 among subjects with baseline Hurley Stage II, comparing izokibep dosed QW to placebo dosed QW or Q2W.
- The fifth secondary endpoint, achieving AN count of 0, 1 or 2 among subjects with baseline Hurley Stage II, comparing izokibep dosed Q2W to placebo dosed QW or Q2W.

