2.3. Sample Size and Power

In Part A, a minimum of 20 subjects and up to 30 subjects will be enrolled. With the minimum of 20 subjects enrolled if the true HiSCR response rate is 50%, an observed rate of 30% to 70% will be observed with 95% probability. Conversely, an observed response rate of 25% or lower suggests that the true rate is < 50% and an observed rate of 75% or higher suggests that the true rate is > 50%, based on limits of a two-sided 95% CI.

For Part B, power calculations were reported in protocol 21102 version 3.0, dated 26 April 2023, for the original primary endpoint of HiSCR50 and not for the updated primary endpoint of HiSCR75. Using the updated primary endpoint of HiSCR75, the comparisons of a regimen of izokibep to placebo will have approximately 55 subjects in each izokibep regimen compared to approximately 55 subjects on placebo (QW and Q2W combined). In prior studies of adalimumab in a similar patient population, a HiSCR75 response rates of 10% to 15% was observed with placebo compared with response rates of 25% to 35% with adalimumab. If true response rates with placebo and izokibep are 15% and 40%, respectively, this study will have approximately 80% power to reject the null hypothesis of equal response rates. This calculation was made in SAS® using the POWER procedure on an unstratified test of binomial proportions.

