6.6.5. Exploratory Analysis

Exploratory endpoints will be analyzed analogously to primary and secondary endpoints with the same strategies for ICEs. Binary endpoints will be analyzed with a stratified test of risk difference and continuous endpoints will be analyzed with an MMRM model in general. Continuous data at timepoints before and including the primary timepoint will use all data from planned assessments up to and including the primary timepoint; continuous data after the primary timepoint will use all data from all planned assessments. Visit week, treatment group and interaction will be included in the MMRM model.

The number and proportion of subjects for binary endpoints in each treatment group will be reported, along with p-values, 95% CI without strata calculated using asymptotic Wald method will be reported as well. Results for continuous endpoints will presented as LS mean changes and associated SEs with associated 95% CI and p-values. For binary endpoints, a line plot showing the proportion of subjects experiencing such endpoints will be produced. For continuous endpoints, a line plot showing the LS mean and SE for each treatment group will be produced. Exploratory endpoint results will also be listed.

The following binary endpoints before or on Week 16 will be analyzed analogously to the primary endpoints of HiSCR75 at Week 16. The number and proportion of subjects for binary endpoints in each treatment group, p-values, 95% CI without strata calculated using asymptotic Wald method will be reported as well. The binary endpoints after week 16 will include number and proportion along with Clopper-Pearson 95% CI without strata according to the four randomized treatment groups. No p-value will be reported.

- HiSCR50, HiSCR75, HiSCR90 and HiSCR100 at Weeks 2, 4, 8, 12, 24 and 32;
- AN count of 0, 1, or 2 at Weeks 4, 8, 12, 24, and 32 among subjects with baseline Hurley Stage II;

- HS flares through Weeks 4 and 32;
- IHS4-55 response rates at Weeks 4, 8, 12, 16, 24 and 32;
- Draining fistula count of 0 at weeks 4, 8, 12, 16, 24 and 32
- Draining fistula count of 0 at weeks 4, 8, 12, 16, 24 and 32, among subjects with baseline draining fistula count of at least 1
- Draining fistula count of 0 at weeks 4, 8, 12, 16, 24 and 32, among subjects with baseline draining fistula count of at least 2

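### At the planned size and a 10-15% placebo rate, the primary test runs at about 5.5-6.2% instead of the stated 4.99%, and single-arm Wald intervals fail when responders are few

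*SAP*

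**What the plan says.** **Level.** SAP 6.6 undertakes to "control the family-wise error rate in the strong sense at $\alpha = 0.050$, two-sided". It adds: "An adjustment of 0.0001 will be made to account for the unblinded data summaries reviewed by the DMC". It concludes: "The hypotheses will therefore be tested at $\alpha = 0.0499". Protocol 9.1.1 makes the same commitment.

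**Test.** SAP 6.6.1 computes a response rate and standard error for each arm within each of the four randomization strata. It combines the risk differences with Cochran-Mantel-Haenszel weights, and then "The estimated risk difference divided by the standard error will be used as the test statistic", with a normal reference distribution. The sample code is `tables stratum * treatment * response / cmh commonriskdiff (test=mh cl=mh)`. SAP 3.1.5 and protocol 9.3.2 describe the same statistic. SAP 6.6.3 carries the approach to HiSCR50, HiSCR90 and HiSCR100, to the AN-count endpoint (without the Hurley factor) and to the pain-response endpoint. Flare is combined over imputed datasets by Rubin's rules.

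**Intervals.** Under SAP 6.6, binary endpoints with non-response imputation "will be presented with 2-sided 95% confidence intervals calculated using asymptotic Wald method". SAP 6.6.5 then changes method: "The binary endpoints after week 16 will include number and proportion along with Clopper-Pearson 95% CI without strata". SAP 6.6.7 mostly follows Clopper-Pearson after Week 16. It returns to Wald for the placebo-randomized subjects who still meet the lesion criteria at Week 16.

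**The concern.** A risk difference divided by a standard error built from each arm's observed rates is a Wald-type statistic. When rates are low and strata are small, that standard error is too small on average and varies with the estimate, so a true null is rejected too often. The trial is described as one of two adequate and well-controlled studies (protocol synopsis and 2.1). The plan gives up 0.0001 of alpha for the DMC's review of unblinded data, yet the choice of variance alone may spend many times that amount. The first test in the fixed sequence is HiSCR75 for QW against pooled placebo, so any excess there is an excess in the familywise error rate.

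The interval problem has the same source. A Wald interval for one proportion has zero width at 0 responders and under-covers at low rates. Such counts are plausible for HiSCR90 and HiSCR100, and in the two placebo schedules (28-29 subjects each), which protocol 9.3.1 also summarizes separately.

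**Working it through.** **Inputs from the documents.** Nominal level 0.05 − 0.0001 = 0.0499, so the two-sided critical value is 1.961. Allocation is 1:1:2:2 with 170 randomized, so each regimen and the pooled placebo have about 56-57 subjects (the sample-size text says about 55). There are four strata. The cited placebo HiSCR75 rate is 10-15%. On power, SAP 2.3 says: "If true response rates with placebo and izokibep are 15% and 40%, respectively, this study will have approximately 80% power".

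**Assumed, because the documents do not say.** Stratum sizes per arm of [23, 17, 11, 6], [15, 14, 14, 14] or [30, 12, 10, 5]; equal arms within strata; the Sato variance for the SAS Mantel-Haenszel option.

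**The plan's own power figure.** With 55 per arm, 15% against 40% and level 0.0499, exact enumeration gives 79.8% for Fisher's test and 79.8% for the continuity-corrected test. The stated 80% is reproduced, but with a more conservative test than the one planned. The pooled normal approximation gives 84.5%.

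**Statistics compared.** In stratum h, let x and y be responders among n₁ active and n₀ placebo subjects, with p₁ = x/n₁, p₀ = y/n₀, N = n₁ + n₀, m = x + y, weight w = n₁n₀/N and W = Σw. The estimate is RD = Σw(p₁ − p₀)/W.

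- Text version: Var = Σw²[p₁(1 − p₁)/n₁ + p₀(1 − p₀)/n₀]/W².
- Sato version: Var = [RD·ΣP + ΣQ]/W², with P = [n₁²y − n₀²x + n₁n₀(n₀ − n₁)/2]/N² and Q = [x(n₀ − y) + y(n₁ − x)]/(2N).
- Stratified CMH score: Σ(x − n₁m/N) divided by the square root of Σ n₁n₀m(N − m)/[N²(N − 1)].

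**Simulated size** (400,000 trials per cell, 57 per arm, nominal 0.0499, range over the three splits):

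| Common true rate | Text version | Sato version | CMH score |
|---|---|---|---|
| 3% | 3.8-3.9% | 3.6-3.7% | 3.4-3.5% |
| 5% | 5.9% | 5.6-5.7% | 4.6-4.7% |
| 10% | 6.0-6.1% | 5.7-5.8% | 4.9% |
| 15% | 6.1% | 5.6% | 4.8-4.9% |
| 20% | 6.1-6.2% | 5.4-5.5% | 4.9% |

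Repeated runs at 10-15% gave 5.5-5.8% (Sato), 6.0-6.2% (text) and 4.8-5.0% (CMH). The excess is therefore between 5.5 − 4.99 ≈ 0.5 and 6.2 − 4.99 ≈ 1.2 points.

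**Checks on the assumptions.** At 55 per arm, with splits from even to 60/25/10/5%, the size at 10-15% was 5.4-5.7% (Sato) and 6.0-6.4% (text). Exact enumeration of the unstratified Wald test, which needs no stratum shares, gives 5.7-6.0% at 10-15%. For the Hurley II subset, assuming 34 per arm in two strata and rates of 10-30%, the sizes are 5.7-5.9% (Sato), 5.9-6.3% (text) and 4.9-5.3% (CMH).

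**Power at 15% against 40%, 57 per arm.** Text version 88%, Sato 87%, CMH 86%.

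**Single-arm intervals (95%).**

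| Responders | Wald | Clopper-Pearson |
|---|---|---|
| 0 of 57 | 0% to 0% | 0% to 6.3% |
| 1 of 57 | −1.7% to 5.2% | 0.04% to 9.4% |
| 0 of 28 | 0% to 0% | 0% to 12.3% |

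The first Clopper-Pearson limit is 1 − 0.025^(1/57) = 0.063. Exact Wald coverage at n = 57 is 44%, 68% and 82% for true rates of 1%, 2% and 3%, and 92-94% for 5-15%. At n = 28 it is 57% at 3% and 76% at 5%. The chance of no responders is (1 − p)ⁿ. At a true rate of 5% this is 5% for n = 57 and 24% for n = 28.

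**The case against.** The strongest reply is that this is a pre-specified large-sample test with an ordinary finite-sample departure. The commitment to strong control introduces the sequential order and is not a claim of exact size. On the code's reading (Sato assumed) the excess at 10-15% is only 0.5-0.8 points. It affects only p-values between about 0.045 and 0.0499, and under the planning alternative the Mantel-Haenszel and CMH decisions differ in about 0.9% of trials. CMH is itself slightly off nominal. All of this stands and limits the size of the point. It does not remove it, because every variant tried exceeds 4.99% at the documents' own placebo rate.

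A reader might infer that every primary and secondary test is inflated. The figures do not support that. At about 3% all versions are conservative, and at 1-2% more so (about 0.3% and 1.8-2.0%). Flare, with multiple imputation, was not assessed. HiSCR50, HiSCR90 and HiSCR100 stand in the protocol's testing sequence (9.1.1) but not in the one in SAP 6.6.

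A reader might also infer that the excess accumulates over the sequence. It does not. In a fixed sequence no false rejection can occur unless the first true null is rejected, so the familywise error is bounded by the size of that one test.

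On intervals, zero width needs exactly 0% or 100% responders. At a 10-15% rate, 0 of 57 has probability 0.25% or less, and the documents give no HiSCR90 or HiSCR100 rates. Several intervals described as Wald without strata (SAP 6.6, 6.6.3, 6.6.5) may be meant for the difference between arms, since the only Wald code, in 6.6.2, is for a difference. The single-arm criticism does not apply to those.

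**Conclusion.** The point holds in limited form. At about 57 per arm, four strata and a 10-15% common rate, the primary test as written has true size of about 5.5-5.8% (Sato variance) or 6.0-6.2% (stratum standard errors in the text), against a stated 4.99%. The same applies to other non-imputed binary tests with null rates of about 5-20%. The excess is 0.5-1.2 points, which is 50 to 120 times the 0.0001 set aside for the DMC review. It rests on assumed stratum shares, near-equal arms within strata and an assumed variance for the SAS option. The direction at 10-15% did not change under any variant.

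Wald intervals for single-arm proportions are unsuitable at low counts, and the SAP already uses Clopper-Pearson for most of its summaries after Week 16. This is worth correcting before unblinding. It does not undermine the design or its power.

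**What to change.** **Test.** In SAP 6.6.1 and 3.1.5, and in protocol 9.3.2 by amendment or a documented change before unblinding, take the p-value for the primary and the non-imputed binary endpoints from the stratified CMH statistic. The `cmh` keyword in the sample code already requests it. Keep the Mantel-Haenszel risk difference and its interval for estimation. Leave flare under Rubin's rules, because a CMH p-value there would need its own combining rule. The cost is about 1-2 points of power (still about 86% at 15% against 40%), an occasional borderline disagreement between p-value and interval, and a protocol-level change as well as SAP wording.

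**Intervals.** In SAP 6.6, and wherever a Wald interval is for one arm's proportion (including the Week 24 and Week 32 subset in 6.6.7), specify Wilson or Clopper-Pearson. State for each interval whether it is for a proportion or a difference, and leave difference intervals as such. The cost is somewhat wider intervals. Clopper-Pearson over-covers, for example 97.7% at n = 57 and 98.8% at n = 28 for a 5% rate.
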